10.3 OTHER CRITERIA

- Not applicable.

11 STATISTICAL ANALYSIS

11.1 JUSTIFICATION OF THE NECESSARY NUMBER OF PATIENTS

The objective of a non-inferiority study is to demonstrate that the mean difference between the 2 devices remains small and clinically insignificant.

The average blood glucose level achieved in real life with the Omnipod pump is 7.8% according to the experience of the three centers in the scientific committee of the study, which is consistent with the literature. We can assume that the average blood glucose level on the Medtrum pump is the same as on the Omnipod pump.

By setting the Δ threshold for non-inferiority at +0.4%, in accordance with FDA recommendations (Guidance for Industry Diabetes Mellitus (Developing Drugs and Therapeutic Biologics for Treatment and Prevention)), if the upper threshold of the IC95% difference between the 2 pumps (Medtrum-Omnipod) exceeds Δ (i.e., 0.4), non-inferiority will not be demonstrated.

Otherwise, the superiority of the Medtrum pump over the Omnipod pump can be tested, with a Δ' threshold set at -0.3%.

Based on these assumptions, based on the so-called "Less is better" design with $\alpha = 2.5\%$, $\beta = 20\%$, and a standard deviation (SD) set at 0.55, the calculation of the necessary number of (analyzable) subjects is 60 patients (30 in each group).

Assuming that 20% of patients cannot be analyzed (major discrepancies, missing data, lost to follow-up), the number of patients to be randomized is 75. The number of centers to be recruited in 3 months maximum is 6.

To confirm our standard deviation hypothesis, a descriptive analysis of the baseline HbA1c data for the entire population will be performed blinded at the end of the inclusion period. If a large difference from our hypotheses is found, the sample size will be recalculated to maintain 80% statistical power for this study.

11.2 STATISTICAL ANALYSIS

11.2.1 *General statistical methods*

Data processing and statistical analysis will be carried out by the service provider, Axonal-Biostatem.

The statistical analyses will be described in a Statistical Analysis Plan (SAP) validated by the Sponsor and the Scientific Committee, prior to the freeze-in.

Statistical analyses will be performed after baseline freezing of the data with SAS® software (SAS Institute, NC, Cary, USA), version 9.4 or later.

Demographic data analyses will be performed in the ITT. Safety analyses will be performed in the Tolerance population. Non-inferiority analyses will be performed in the Per Protocol population and validated in the ITT population.

For quantitative variables, the usual statistics (n, missing n, mean, standard deviation (SD), median, first and third quartiles (Q1 and Q3), minimum and maximum) will be presented.

IC95% may be presented if relevant (especially for the primary endpoint).

For categorical variables, the usual statistics (n, missing n, frequency and percentage) of each modality will be provided.

Descriptive statistics will be provided in aggregate.

The type 1 error, α , is set at 5% for all analyses.

11.2.2 Study populations

To meet the study objectives, 2 populations will be defined:

- ITT: all included patients who used the pump device at least once. Patients will be analyzed according to their group allocated by randomization.
- Per Protocol: ITT patients with no major protocol deviations.
- Tolerance population: all patients who have used the pump device at least once.

11.2.3 Descriptive Analysis

All variables collected will be described and/or listed as individual data.

Efficacy and safety variables will be analyzed according to the sections below (11.2.4 and 11.2.5). Socio-demographic, clinical, medical history and treatment characteristics will be described according to the methodology presented in section 11.2.1.

11.2.4 Analysis of the effectiveness / performance of the device

Analysis of primary efficacy endpoint:

The non-inferiority analysis of the primary efficacy endpoint will be performed with an ANOVA, with the DM as an explanatory variable, on the *per protocol* population and then on the *intention-to-treat* population. If the upper bound of the IC95% of the Omnipod-Medtrum estimated difference in means (LSmeans) exceeds the non-inferiority bound, it will be rejected.

Non-inferiority bounds are defined in this protocol and will be used in the statistical analysis plan.

If non-inferiority is demonstrated, a superiority analysis will be conducted.

Secondary efficacy endpoint analyses:

The secondary efficacy endpoints will be analyzed for the variables listed below.

Each variable will be described globally and by pump group.

In case of non-inferiority analysis, the same methodology as for the primary endpoint will be used.

In case of comparison of quantitative variables, parametric (T-test) or non-parametric (Mann-Whitney) tests of comparison of means will be used. In case of comparison of qualitative variables, CHI² or Fisher exact tests will be used.

In case of tests on changes within each group, paired data tests will be used (paired data T-test or Wilcoxon signed ranks test, depending on the distribution of the data).

❖ **HbA1c:**

- Evolution of the value measured in the laboratory from a blood sample taken before the D0 visit and just before the 3-month visit
- Description in the total population, in each group and comparison between groups.

❖ **Glucose measurements**

- Average of glucose measurements over each period and over the entire study duration
- Description of the minimum and maximum values over the total duration of the study
- Description of the % of Time in Range (see ADA and International Consensus on Time in Range recommendations^{25,26})
- Description in the total population, in each group and comparison between groups.

❖ **Glycemic events**

- Description of the number of symptomatic and non-symptomatic hypoglycemic events during the evaluation period, broken down by severity level (see ADA consensus definitions²⁵)
- Description of the number of symptomatic and non-symptomatic hyperglycemia events during the evaluation period, broken down by severity level (see ADA consensus definitions²⁵)
- Description in the total population, in each group and comparison between groups.
-

❖ **Device tolerance**

- Description of local skin tolerance at the pump site and at the FreeStyle Libre blood glucose sensor site).
- Description of any local or systemic safety issues reported during the study, including the additional one-month phase at the end of the study for patients in the "Omnipod" arm
- Description in the total population, in each group and comparison between groups of the number of patients who had at least one tolerance problem.

❖ **Incidents with devices**

- Description of any type of incident involving the operation of the medical devices used, particularly for pumps: pulling out, control problems, transmission difficulties, obstructions, leaks, etc.
- Description in each group, in the overall population and comparison between groups

❖ Patient satisfaction

- Description of the responses to the self-questionnaire assessing satisfaction with the use of the device (pump+PDM), in each group and in the total population
- Comparison of responses between groups
- Description of responses to the final question regarding patient preference between the Medtrum device and the Omnipod device: in each group and in the total population

❖ Insulin treatment

- Description of insulin doses delivered
- Description of any additional insulin injections with a pen during the study
- Description in the total population, in each group and comparison between groups

11.2.5 Tolerance analyses:

The analyses will be performed on the tolerance population.

Prior to any analysis all DM-related incidents and DM-related tolerance will be coded by the MedDRA regulatory medical dictionary (version 20.0 or later).

A summary table (number and percentage of patients with an AE and number of events) by organ system class (OSG) and preferred term (PT) will be presented for the following categories of events by dissociating DM-related incidents and tolerance:

- According to the link (device AND procedure),
- Depending on the link (device OR procedure),
- Depending on the severity,
- Depending on the actions taken (de-pairing).

A listing of individual data will be provided describing all the information collected via the eCRF concerning the IS (including duration, resolution, severity criteria, linkage, severity etc.)

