4.4.2 Secondary endpoints

The secondary endpoints were:

- HbA1c:
 - Value measured in the laboratory from a blood sample taken before the D0 visit and just before the 3-month visit
- Glucose Level Measurements
 - Average of glucose measurements over each time period and over the entire study duration
 - Minimum and maximum values
 - Time in range expressed as a %.

These values were automatically calculated by the FreeStyle Libre software and will be reported by the investigator.

- Glycemic events
 - Number of symptomatic and non-symptomatic hypoglycemic events during the evaluation period, broken down by severity level
 - Number of symptomatic and non-symptomatic hyperglycemia events over the evaluation period, broken down by severity level

This information was derived from the Free Freestyle data and the data entered by the patient in the MDP.

The definition of hypoglycemia and hyperglycemia is the ADA consensus definition:

Table 1—Summary of consensus definitions			
Outcome	Definition		
Hypoglycemia	Level 1: glucose <70 mg/dL (3.9 mmol/L) and glucose \geq 54 mg/dL (3.0 mmol/L) Level 2: glucose <54 mg/dL (3.0 mmol/L) Level 3: a severe event characterized by altered mental and/or physical status requiring assistance		
Hyperglycemia	Level 1—elevated glucose: glucose $>$ 180 mg/dL (10 mmol/L) and glucose \leq 250 mg/dL (13.9 mmol/L) Level 2—very elevated glucose: glucose $>$ 250 mg/dL (13.9 mmol/L)		
Time in range	Percentage of readings in the range of 70–180 mg/dL (3.9–10.0 mmol/L) per unit of time		

- Device tolerance
 - Local skin tolerance at the pump site (adhesive hold) and at the FreeStyle Libre blood glucose sensor site (adhesive hold)
 - Any local or systemic safety issues were to be reported during the study, including the additional one-month phase at the end of the study for patients in the Omnipod group
- Incidents with devices
 - Any type of incident involving the operation of the medical devices used, especially for pumps: pulling out, control problems, transmission difficulties, occlusion, leakage, etc.
- Patient satisfaction
 - Self-questionnaire evaluating satisfaction with the use of the device (pump + PDM)

- Final question regarding patient preference between the Medtrum device and the Insulet device
- Insulin treatment
 - The insulin treatment used should be documented

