4.4.3 Calculated/derived criteria

			2 = "More than 10 years
Number of years and months of treatment per pump	PUMP_D = Number of years * 12 + number of months	Time since starting pump therapy (in months)	Digital
Weight (kg) and height (cm)	BMI_D = (weight/height ²)*10000	Body Mass Index (BMI)	Digital
IMC_D	IMC4CL_D = -0 if BMI_D<18.5 -1 if BMI_D = [18,5 ; 25[-2 if BMI_D = [25; 30[. -3 if BMI_D >= 30	BMI (in classes)	0 = "Less than 18.5 1 = " [18,5 ; 25[" 2 = " [25 ; 30[" 3 = "Greater than 30
Tolerance variables	AL_PBTOL_D = -1 if the patient reported during the follow-up an irritation/itching problem or a redness problem or another adverse event -0 otherwise	Patient with at least one tolerance problem	0 = "No 1 = "Yes
HbA1c value measured in the laboratory at D0 and 3M	EVOL_HBA1C_D = HbA1c at M3 - HbA1c at D0	Evolution of HbA1c between D0 and 3M	Digital
Estimated HbA1c (FSL) (%)	EVOL_eHbA1c = HbA1c estimate at V2 - HbA1c estimate at D0 (will also be calculated for V3 and V4)	Evolution of HbA1c estimation between D0 and V2,V3,V4	Digital
Average blood glucose at different follow-up times	EVOL_GLYC_V2 = Average blood glucose at V2 - Average blood glucose at D0 (will also be calculated for V3 and V4)	Evolution of the average blood glucose level between D0 and V2, V3, V4	Digital
Average daily basal dose at different follow-up times	EVOL_BASAL_V2 = Average daily basal dose at V2 - Average daily basal dose at D0 (will also be calculated for V3 and V4)	Evolution of the average daily basal dose between D0 and V2, V3, V4	Digital
Average daily bolus dose at different follow-up times	EVOL_BOLUS_V2 = Average daily bolus dose at V2 - Average daily bolus dose at D0 (will also be calculated for V3 and V4)	Evolution of the average daily bolus dose between D0 and V2, V3, V4	Digital

Number of Boluses/day at different follow-up times	EVOL_NB_BOLUS_V2 = Number of Boluses/day at V2 - Number of Boluses/day at D0 (will also be calculated for V3 and V4)	Evolution of the number of Bolus/day between D0 and V2, V3,V4	Digital
Time of wearing the FSL	PORT_70sup = -1 wear time greater than 70%. -0 otherwise	FSL wear time greater than 70%.	0 = "No 1 = "Yes

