7.5 ANALYSIS OF TOLERANCE DURING THE STUDY

Analyses will be performed overall and by pump group on the **tolerance population**. Prior to any analysis, all DM-related incidents and DM-related tolerance will be coded by the MedDRA regulatory medical dictionary (version 20.0 or later).

The number of patients who had at least one tolerance problem will be described. The following criteria will be described for each period and by pump group:

- Irritation/itching (yes; no)
 - If yes, maximum intensity (low; moderate; intense)
- Redness (yes; no)
 - If yes, maximum intensity (low; moderate; intense)
- Other adverse events (yes; no)
 - All other events related to tolerance will be given in a listing.

A summary table (number and percentage of patients with AEs and number of events) by organ system class (OSG) and preferred term (PT) will be presented for the following categories of events by dissociating incidents and tolerance related to the medical device:

- According to the link (device AND procedure)
- According to the link (device OR procedure)
- Depending on the severity
- Depending on the actions taken (de-boosting)

A listing of individual data will be provided describing all the information collected via the eCRF concerning the AE (including duration, resolution, severity criteria, linkage, severity etc.)

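### Two cumulative tolerance outputs have no V3 cut-off, so A7+ events from the optional extension month may be counted under Omnipod

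*Protocol*

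**What the plan says.** **Who is exposed after V3.** The protocol summary (duration of follow-up) lets Omnipod-arm patients use the A7+ for one month after the 3-month visit if they wish. Medtrum-arm patients return their equipment at V3 (Protocol 7.5). Protocol 7.6 collects tolerance data and adverse events at V4, from Omnipod-arm patients only.

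**What counts as tolerance.** Under device tolerance, Protocol 11.2.4 gives the scope of the safety description as follows: "safety issues reported during the study, including the additional one-month phase at the end of the study for patients in the" (the sentence ends by naming those randomised to Omnipod). The next bullet plans a "comparison between groups of the number of patients who had at least one tolerance problem". SAP 4.4.2 repeats the scope: tolerance issues are to be reported "including the additional one-month phase at the end of the study for patients in the Omnipod group".

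**How the SAP derives and reports it.** In SAP 4.4.3, AL_PBTOL_D equals 1 "if the patient reported during the follow-up an irritation/itching problem or a redness problem or another adverse event"; no visit is named. SAP 7.5 works overall and by pump group on the tolerance population. It says: "The number of patients who had at least one tolerance problem will be described". For irritation/itching, redness and other adverse events it says: "The following criteria will be described for each period and by pump group". It then asks for SOC/PT summary tables and mentions no period for them. The SOC/PT template in SAP 8 has a single Total column.

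**Grouping.** Protocol 11.2.2 states analysis by allocated group for the ITT population only. Neither that section nor SAP 7.1.3 gives such a rule for the tolerance population.

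**The concern.** In the extension month an Omnipod-arm patient wears the sponsor's pump. If a skin reaction in that month enters a cumulative count under the randomised label, two things happen at once: an A7+ event is credited to Omnipod, and the Omnipod group is observed for longer. Both raise the Omnipod figure and make the A7+ look better by comparison. This would affect the between-group tolerance comparison planned in Protocol 11.2.4. SAP section 6 declares no change to the protocol's analyses, so that comparison still stands although SAP 7.5 only describes the count. Collecting safety and tolerance data on the A7+ is a stated aim (Protocol 2.2).

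**Working it through.** **1. Which window does the text support?**

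- *Ending at V3.* The protocol summary gives follow-up as 3 months from randomisation. Protocol 2.1 lists the 12 weeks of follow-up and the extra month as separate items. Protocol 7.5 and 7.6 call V3 the end-of-study visit and place V4 after the end of the study.
- *Including V3–V4.* Protocol 11.2.4 and SAP 4.4.2 name the extra month under tolerance. The table that defines AL_PBTOL_D also has a row with source data "Average blood glucose at different follow-up times" and label "Evolution of the average blood glucose level between D0 and V2, V3, V4", which treats V4 as a follow-up time.

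Both readings are open, so two programmers could produce different counts from the same text.

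**2. Exposure and event counts.** The documents give no tolerance rate and no expected uptake, so there is no planned figure to reproduce. The inputs are 12 weeks per arm (Protocol 2.1) and 4 further weeks for Omnipod-arm patients who accept (Protocol 7.6). Let u be the share who accept (assumed). With equal arm sizes and equal weekly rates on both pumps:

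- ratio of Omnipod-group to Medtrum-group events = (12 + 4u)/12
- share of Omnipod-group events that occurred on the A7+ = 4u/(12 + 4u)

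| u | Event ratio | A7+ share of Omnipod-group events |
|---|---|---|
| 0 | 1.00 | 0% |
| 0.5 | 14/12 = 1.17 | 2/14 = 14% |
| 0.8 | 15.2/12 = 1.27 | 3.2/15.2 = 21% |
| 1 | 16/12 = 1.33 | 4/16 = 25% |

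**3. Patients with at least one problem.** Assume a 12-week risk p that is the same on both pumps, constant hazard, and extension risk independent of the first 12 weeks. The 4-week risk is q = 1 − (1 − p)^(1/3). The Omnipod group then reads 1 − (1 − p)(1 − uq).

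| True p, both arms | q | Omnipod reads, u = 0.5 | Omnipod reads, u = 1 | False excess, u = 1 |
|---|---|---|---|---|
| 10% | 0.0345 | 11.6% | 13.1% | 3.1 points |
| 20% | 0.0717 | 22.9% | 25.7% | 5.7 points |
| 30% | 0.1121 | 33.9% | 37.8% | 7.8 points |

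Take 50 per arm (100 included, 1:1) and an uncorrected two-sided chi-square test at 5%. At full uptake the chance of a significant difference between equal pumps is then about 8%, 11% and 13% in the three rows, against about 5% with equal windows.

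**4. If the A7+ is truly worse.** Assume 12-week risks of 30% on the A7+ and 20% on Omnipod, so q = 0.1121. The Omnipod group reads 1 − 0.8(1 − 0.1121u): 24.5%, 27.2% and 29.0% at u = 0.5, 0.8 and 1. The true 10-point gap shrinks to 5.5, 2.8 and 1.0 points.

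**The case against.** The best case against has four parts.

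- **Follow-up means 12 weeks.** The passages in step 1 make D0–V3 a natural reading of AL_PBTOL_D. In Protocol 11.2.4 the extension and the group comparison are in separate bullets. This stands as far as it goes: it is not settled that extension events will be counted. It does not remove the ambiguity, because the tolerance endpoint itself is defined to include the extra month.
- **Pump group may mean pump worn.** SAP 7.3 speaks of the group allocated by randomisation, while SAP 7.5 speaks only of pump group. If pump worn is meant, A7+ events would not fall under Omnipod. Extension patients would then belong to both columns with unequal exposure, and no denominator is given. A rule is needed either way.
- **The components are already split by period.** SAP 7.5 gives irritation, redness and other events by period, and SAP 7.4.2 treats V3–V4 as its own period for glucose. An individual listing is also planned. A reader might infer that every by-group tolerance output is affected, or that an A7+ excess would be hidden. The documents do not support either, because the excess could be seen in those tables. What remains is the summary count and the SOC/PT tables. Patient counts by period cannot be added up to a D0–V3 count, since one patient can appear in several periods.
- **The sizes are assumed.** This is correct. If patients with sensitive skin react to both adhesives, those free of problems at V3 are at lower risk, and the patient-level effect is smaller than shown.

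**Conclusion.** The point holds for two outputs: the count of patients with at least one tolerance problem, with its between-group comparison, and the by-group SOC/PT tables. For these the plan brings the A7+ extension month into tolerance without a V3 cut-off or an attribution rule. If the extension is counted by randomised arm, the comparison is biased in favour of the A7+. The exposure ratio of up to 1.33 follows from the visit schedule. The patient-level figures depend on assumed risks, uptake, constant hazard and independence, and the bias is zero if nobody enters the extension. It would be too strong to say that the plan definitely counts these events under Omnipod, or that its safety reporting as a whole is compromised. The primary endpoint and the period tables of irritation, redness and other events are not affected. The change should be made before the freeze, as a clarification of secondary safety outputs.

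**What to change.** In SAP 4.4.3 and 7.5:

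1. Restrict AL_PBTOL_D, its between-group comparison and the by-group SOC/PT tables to D0–V3, by randomised group.
2. Report V3–V4 events in a separate column headed A7+ extension, with the number of patients entering the extension as denominator. Adapt the SOC/PT template in SAP 8 to show these columns.
3. Assign events to the window by onset date, or by the reporting visit if that date is incomplete. The imputation rule in SAP 5.3 (missing day set to 15) could otherwise move an event across V3.

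The cost is a few lines of SAP text and minor reprogramming. Onset date and time are already recorded (Protocol 13.2.1) and adverse events are collected visit by visit (Protocol 7.2). No new data, visits or patients are needed.

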11.2.6 Intermediate analysis

No interim analysis is planned.

On the other hand, a descriptive analysis of the baseline HbA1c data for the whole population will be performed in a blinded fashion at the end of the inclusion period, in order to confirm or not the standard deviation hypothesis planned for the non-inferiority analysis. As this analysis is purely descriptive no α -risk adjustment is planned.

11.2.7 Subgroup analyses , exploratory analyses

They will eventually be described in the final statistical analysis plan.

12 QUALITY CONTROL

Monitoring

This study will be followed at all stages of its realization by CRAs of the service provider company (AXONAL-BIOSTATEM) mandated by the Developer.

This clinical study will be conducted according to the good practices of the ISO 14155 standard and if applicable according to the ICH-GCP E6(R2) recommendations.

The contractor's ARCs will be responsible for the set-up, monitoring and closing of the centers.

At the time of study implementation, the CRA will provide training on the content of the protocol and the eCRF to participating physicians. Training of the centers on the use of the medical device will be conducted by an authorized representative of the Sponsor.

At the Sponsor's request, site visits may also be conducted on a regular basis according to a set schedule. During these visits, the investigator will allow the CRA direct access to the various study documents: observation booklet, informed consent, investigator's binder and source documents, in a confidential manner. During these visits, the CRA will check the patient information and consent forms, will be able to compare the data recorded in the eCRFs with the source data (missing data, outliers), and will ensure that the study is conducted in compliance with the protocol and Good Clinical Practices (GCP).

The CRA will also verify, at each visit, that all adverse events (AEs) and in particular serious adverse events (SAEs) that may have been observed during the study are reported within the specified time frame.

At the end of the study a close-out visit will be conducted, and the CRA will arrange for the return of used/unused medical devices to the Sponsor.

Audits /Inspections

At the Sponsor's request, audits may be conducted to verify the quality of the data, their authenticity and compliance with the procedures outlined in the protocol. Where appropriate, these audits will be conducted during the course of the study and/or at the end of the study by auditors independent of the team responsible for the implementation and monitoring of the study.

In addition, representatives of the French health authorities, as well as those of the Comité de Protection des Personnes, may inspect the investigating centers at any time. If the investigator is aware of such an audit, he/she should immediately inform the sponsor.

The investigator should ensure that he/she is available on the day of the audit/inspection and that the auditors have free access to all source documents.

